9.4.3 Secondary Analysis (or Analysis of Secondary Endpoints)

The time to local failure will be defined from the date of randomization to the date of biopsy proven recurrence within the prostate gland. The distribution of the time to event data will be estimated by Kaplan-Meier method.

The time to clinical progression will be defined from the date of randomization to the date of PSA failure, local failure, regional or distant metastases. Deaths prior to any of these events are treated as censoring for this endpoint. The distribution of the time to event data will be estimated by Kaplan-Meier method.

To assess PSA nadir, PSA, testosterone levels, HbA1c, fasting glucose, fasting insulin and fasting lipid and cholesterol levels at each time point, the summary statistics for continuous variables will be used.

To assess their changes across the time, the random effect model for longitudinal data will be used for each outcome measurement.

Patient-reported quality of life outcomes will be assessed by EPIC, PROMIS, and EQ-5D questionnaires and will be described by summary statistics for categorical data.

10 Study Management

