2.2 Secondary

1. To determine time to biochemical failure as determined by the ASTRO Phoenix definition of nadir + 2 ng/mL, local progression, regional progression, and distant metastases.
2. To determine time to clinical progression free survival
3. To assess PSA nadir and PSA and testosterone levels at 3-4, 6, 12, and 24 months.
4. To assess changes in HbA1c, fasting glucose, fasting insulin and fasting lipid and cholesterol levels.

5. To document changes in quality of life outcomes.

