2.4.2 Secondary Endpoints

1. PSA and testosterone measurements will be made at 6 weeks and then at 3-4 months, 6 months, 12 months, 18 months, 24 months, and at 36 months as part of standard of care. The time to biochemical failure will be defined from the date of randomization to the date of a rise by ≥ 2 ng/mL from the nadir PSA per the Phoenix Definition. PSA nadir and PSA and testosterone levels will be documented at 4, 6, 12, and 24 months.
2. The time to local failure will be defined from the date of randomization to the date of biopsy proven recurrence within the prostate gland.
3. The date of regional or distant metastases will be defined as the date from randomization to the date of imaging or biopsy demonstrated evidence for recurrence in the pelvic lymph nodes (regional) or systemically. Biopsy is not required to define regional or distant metastasis; however, in absence of rising PSA, biopsy is encouraged.
4. The time to clinical progression will be defined from the date of randomization to the date of PSA failure, local failure, regional or distant metastases. Deaths prior to any of these events are treated as censoring for this endpoint.
5. Changes in HbA1c, fasting glucose, fasting insulin and fasting lipid and cholesterol levels will be assessed at 12 and 24 months during treatment.
6. Quality of life will be monitored. Changes in patient reported quality of life would be measured by the Expanded Prostate Cancer Index Composite (EPIC).

Changes in fatigue from baseline to 1 year will be measured by PROMIS. Assessment of quality adjusted survival will be performed using the EQ-5D.

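### Section 9.4.3 gives EPIC, PROMIS and EQ-5D only categorical description, which matches none of their stated endpoints: change on EPIC, one-year change in PROMIS fatigue, quality-adjusted survival from EQ-5D

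*Combined protocol and SAP*

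**What the plan says.** The objective in section 2.2 is "To document changes in quality of life outcomes". Section 2.4.2 makes it specific by instrument. EPIC is to measure change, with no reference time given. For PROMIS, "Changes in fatigue from baseline to 1 year will be measured by PROMIS". For the EQ-5D the target is different: "Assessment of quality adjusted survival will be performed using the EQ-5D".

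Section 9.4.3 then sets out the analysis in three steps. PSA nadir, PSA, testosterone, HbA1c, glucose, insulin, lipids and cholesterol come first, in a sentence that ends "fasting lipid and cholesterol levels at each time point, the summary statistics for continuous variables will be used". Next comes "To assess their changes across the time, the random effect model for longitudinal data will be used for each outcome measurement". The questionnaires follow in a sentence of their own: "Patient-reported quality of life outcomes will be assessed by EPIC, PROMIS, and EQ-5D questionnaires and will be described by summary statistics for categorical data".

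Section 9 says nothing more about quality of life. It gives no change score, category cut-off, visit contrast, confidence interval or method for quality-adjusted survival.

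**The concern.** Two of the three endpoints are changes within patients, and the third is a quantity accumulated over survival time. A categorical description is neither. If the plan is followed literally, the report will contain tables of categories. It will contain no estimate of how much fatigue changed by one year, no statement of its uncertainty, and no quality-adjusted survival. Because no categories are defined, cut-offs could also be chosen after the data are seen.

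This has some weight in this trial. Safety and feasibility are a primary objective (section 2.1), section 1.2 lists fatigue among the adverse events of enzalutamide, and PROMIS is the only instrument assigned to change in fatigue.

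**Working it through.** The plan states no figure for quality of life, so there is none to reproduce. The check is mainly a comparison of text, with three short calculations.

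**1. Endpoint against analysis.**

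| Instrument | Endpoint (2.4.2) | What it requires | What 9.4.3 supplies |
|---|---|---|---|
| EPIC | Change, reference time not stated | A change score or visit contrast | Categorical description; no categories of change defined |
| PROMIS | Fatigue, baseline to one year | The same, at a named visit | The same |
| EQ-5D | Quality-adjusted survival | A numeric value per visit, applied over survival time | Categorical description; no weighting |

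**2. Does the random effect model cover the questionnaires?** The word *their* in the model sentence points back to the laboratory variables listed just before it. Those variables are declared continuous. The questionnaires come after the model sentence and are given a different data type. On the ordinary reading, the model does not reach them.

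**3. What category percentages at two visits reveal about change.** The percentages here are assumed for illustration. Let p0 = 60% of patients be above some cut-off at baseline and p1 = 50% at one year. The share who moved from above to below lies between max(0, p0 − p1) = 10% and min(p0, 1 − p1) = min(60%, 50%) = 50%. Percentages by visit therefore do not identify within-patient change, and they do not identify the mean change in score.

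**4. What a continuous paired analysis would deliver.** Section 9.2.1 gives 53 patients with 10% dropout: 53 × 0.9 = 47.7, and the same section uses 47. The documents give no SD, so the result is in units of the SD of change. The 95% half-width is t(0.975, n − 1)/√n.

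- n = 47: 2.013/6.856 = 0.29 SD
- n = 53: 2.007/7.280 = 0.28 SD

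**5. Are the data there, and when is one year?** Questionnaires are scheduled before enrolment (3.1, 6.1.1), before radiotherapy and after 5 weeks of pelvic radiotherapy (6.1.3), and at each follow-up visit (6.1.4, Table 6). The data needed for change will therefore exist.

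Follow-up months are counted from completion of radiotherapy (3.6, 6.1.4). Radiotherapy starts about 8 weeks after the first injection (section 4), and the pelvic phase lasts 5 weeks. The month-12 visit therefore falls about 8 + 5 + 52 = 65 weeks after the start of hormone therapy, and later if the boost takes further weeks. One year from the start of hormone therapy would be about 52 − 13 = 39 weeks after pelvic radiotherapy. That lies between the month-6 visit (26 weeks) and the month-12 visit (52 weeks), and outside the ±14-day window of either. The PROMIS contrast is not defined until the visit is named.

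**The case against.** The strongest reply is that little is at stake. The objective is to document change, which is a descriptive aim. The trial is a single-arm study sized on PSA complete response, and no decision or stopping rule uses a questionnaire score. Preferring a model to a description is partly a matter of taste. This stands as a limit on importance, but it does not supply the missing analysis of three named endpoints.

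A second reply is that "the random effect model for longitudinal data will be used for each outcome measurement" may have been meant to include the questionnaires. That is possible but weak, given the pronoun, the order of the sentences and the contrast between continuous and categorical data. If it was intended, one clause would settle it.

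A third reply concerns a stronger reading. A reader might infer that the planned method makes change impossible to estimate. The documents do not support that. Change can be classed as improved, stable or worse and still be summarised as categorical data with the pairing kept, and the questionnaires are collected at baseline and follow-up. What is true is narrower: the plan defines no such categories and specifies no analysis of change.

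Finally, the documents do not describe how the instruments are scored or which PROMIS form is used. This also stands, and the fix should cover it.

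**Conclusion.** The concern holds in limited form. The stated analysis matches none of the three quality-of-life endpoints: it yields no estimate or interval for change on EPIC or PROMIS, and no numeric weighting of time for the EQ-5D. This is more than missing detail, because a method is stated and it does not fit the targets. The consequence is confined to a secondary, descriptive objective; the primary analysis and sample size do not change.

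Three further inferences go beyond the documents:

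- **That all three endpoints are change from baseline.** Only PROMIS fatigue names baseline. EPIC gives no reference time, and the EQ-5D endpoint is quality-adjusted survival.
- **That a definite loss of information can be quoted.** No cut-offs or number of categories are planned, so no percentage loss follows. Nor would ignoring the pairing make the estimate itself more variable. With the same patients at both visits, the difference of visit means equals the mean paired difference, and only the calculated standard error would be too large. The plan proposes no standard error here.
- **That dropout is handled by analysing whoever attends.** The plan does not say how missing questionnaires are treated.

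The conclusion rests on reading the model sentence as covering the laboratory variables only. The recommendation also assumes that the EPIC domains, PROMIS fatigue and the EQ-5D yield numeric scores. The documents imply this only for the EQ-5D, through quality-adjusted survival.

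**What to change.** Amend section 9.4.3 as follows:

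- Name the scores and treat them as continuous: EPIC domain scores, the PROMIS fatigue score (stating the form used) and the EQ-5D index.
- Extend the existing random effect model to these scores, with visit as a factor, and report mean change from baseline with 95% confidence intervals.
- Name PROMIS fatigue at one year as the contrast of interest, and state which scheduled visit counts as one year, since month 12 runs from completion of radiotherapy.
- Derive quality-adjusted survival from the EQ-5D index over follow-up time, stating the time horizon and how death and incomplete follow-up enter.
- Keep categorical summaries as description, with any cut-offs fixed in advance.

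The cost is a few sentences and a little more analysis work. The questionnaires are already scheduled, and no visit, sample size or primary analysis changes.

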10.1 Pre-study Documentation

This study will be conducted in accordance with the ethical principles that have their origin in the Declaration of Helsinki as stated in 21 CFR §312.120(c)(4); consistent with GCP and all applicable regulatory requirements.

Before initiating this trial, the Investigator will have written and dated approval from the Institutional Review Board for the protocol, written informed consent form, subject recruitment materials, and any other written information to be provided to subjects before any protocol related procedures are performed on any subjects.

The clinical investigation will not begin until either FDA has determined that the study under the Investigational Drug Application (IND) is allowed to proceed or the Investigator has received a letter from FDA stating that the study is exempt from IND requirements.

The Investigator must comply with the applicable regulations in Title 21 of the Code of Federal Regulations (21 CFR §50, §54, and §312), GCP/ICH guidelines, and all applicable regulatory requirements. The IRB must comply with the regulations in 21 CFR §56 and applicable regulatory requirements.

10.2 Institutional Review Board Approval

The protocol, the proposed informed consent form, and all forms of participant information related to the study (e.g. advertisements used to recruit participants) will be reviewed and approved by the UCSF CHR (UCSF Institutional Review Board). Prior to obtaining CHR approval, the protocol must be approved by the Helen Diller Family Comprehensive Cancer Center Site Committee and by the Protocol Review Committee (PRC). The initial protocol and all protocol amendments must be approved by the IRB prior to implementation.

10.3 Informed Consent

All participants must be provided a consent form describing the study with sufficient information for each participant to make an informed decision regarding their participation. Participants must sign the CHR-approved informed consent form prior to participation in any study specific procedure. The participant must receive a copy of the signed and dated consent document. The original signed copy of the consent document must be retained in the medical record or research file.

10.4 Changes in the Protocol

Once the protocol has been approved by the UCSF CHR, any changes to the protocol must be documented in the form of an amendment. The amendment must be signed by the Investigator and approved by PRC and the CHR prior to implementation.

If it becomes necessary to alter the protocol to eliminate an immediate hazard to patients, an amendment may be implemented prior to CHR approval. In this circumstance, however, the Investigator must then notify the CHR in writing within five (5) working days after implementation. The Study Chair and the UCSF study team will be responsible for updating any participating sites.

10.5 Handling and Documentation of Clinical Supplies

The UCSF Principal Investigator and each participating site will maintain complete records showing the receipt, dispensation, return, or other disposition of all investigational drugs. The date, quantity and batch or code number of the drug, and the identification of patients to whom study drug has been dispensed by patient number and initials will be included. The sponsor-investigator will maintain written records of any disposition of the study drug.

The Principal Investigator shall not make the investigational drug available to any individuals other than to qualified study patients. Furthermore, the Principal Investigator will not allow the investigational drug to be used in any manner other than that specified in this protocol.

10.6 Case Report Forms (CRFs)

The Principal Investigator and/or his/her designee, will prepare and maintain adequate and accurate participant case histories with observations and data pertinent to the study. Study specific Case Report Forms (CRFs) will document safety and treatment outcomes for safety monitoring and data analysis. All study data will be entered into OnCore® via standardized CRFs in accordance with the CTMS study calendar, using single data entry with a secure access account. The Clinical Research Coordinator (CRC) will complete the CRFs as soon as possible upon completion of the study visit; the Investigator will provide oversight.

The information collected on CRFs shall be identical to that appearing in original source documents. Source documents will be found in the patient's medical records maintained by UCSF personnel. All source documentation should be kept in separate research folders for each patient.

In accordance with federal regulations, the Investigator is responsible for the accuracy and authenticity of all clinical and laboratory data entered onto CRFs. The PI will approve all completed CRFs to attest that the information contained on the CRFs is true and accurate.

All source documentation and CTMS data will be available for review/monitoring by the UCSF DSMC and regulatory agencies.

The Principal Investigator will be responsible for ensuring the accurate capture of study data. At study completion, when the CRFs have been declared to be complete and accurate, the database will be locked. Any changes to the data entered into the CRFs after that time can only be made by joint written agreement among the Study Chair, the Trial Statistician, and the Protocol Project Manager.

Each participating site will complete study specific CRFs for safety monitoring and data analysis. Each site will enter the study data into OnCore® via standardized CRFs in accordance with the CTMS study calendar, using single data entry with a secure access account. The participating site's Clinical Research Coordinator (CRC) will complete the

CRFs; the Investigator will review and approve the completed CRFs – this process must be completed within 10 business days of the visit. Study data from the participating site will be reported and reviewed in aggregate with data from patients enrolled at the coordinating center, UCSF. All source documentation and CTMS data will be available for review/monitoring as needed.

10.7 Oversight and Monitoring Plan

The UCSF Helen Diller Family Comprehensive Cancer Center DSMC will be the monitoring entity for this study. The UCSF DSMC will monitor the study in accordance with the NCI-approved Data and Safety Monitoring Plan (DSMP). The DSMC will routinely review all adverse events and suspected adverse reactions considered “serious”. The DSMC will audit study-related activities to ensure that the study is conducted in accordance with the protocol, local standard operating procedures, FDA regulations, and Good Clinical Practice (GCP). Significant results of the DSMC audit will be communicated to the IRB and the appropriate regulatory authorities at the time of continuing review, or in an expedited fashion, as applicable. See Appendix 2 Data and Safety Monitoring Plan for a Phase 2 or 3 Institutional Study, for additional information.

10.8 Record Keeping and Record Retention

The Principal Investigator is required to maintain adequate records of the disposition of the drug, including dates, quantity, and use by subjects, as well as written records of the disposition of the drug when the study ends.

The Principal Investigator is required to prepare and maintain adequate and accurate case histories that record all observations and other data pertinent to the investigation on each individual administered the investigational drug or employed as a control in the investigation. Case histories include the case report forms and supporting data including, for example, signed and dated consent forms and medical records including, for example, progress notes of the physician, the individual's hospital chart(s), and the nurses' notes. The case history for each individual shall document that informed consent was obtained prior to participation in the study.

Study documentation includes all CRFs, data correction forms or queries, source documents, Sponsor-Investigator correspondence, monitoring logs/letters, and regulatory documents (e.g., protocol and amendments, CHR correspondence and approval, signed patient consent forms).

Source documents include all recordings of observations or notations of clinical activities and all reports and records necessary for the evaluation and reconstruction of the clinical research study.

In accordance with FDA regulations, the investigator shall retain records for a period of 2 years following the date a marketing application is approved for the drug for the indication for which it is being investigated; or, if no application is to be filed or if the application is not approved for such indication, until 2 years after the investigation is discontinued and FDA is notified.

11 Protection of Human Subjects

11.1 Protection from Unnecessary Harm

Each clinical site is responsible for protecting all subjects involved in human experimentation. This is accomplished through the CHR mechanism and the process of informed consent. The CHR reviews all proposed studies involving human experimentation and ensures that the subject's rights and welfare are protected and that the potential benefits and/or the importance of the knowledge to be gained outweigh the risks to the individual. The CHR also reviews the informed consent document associated with each study in order to ensure that the consent document accurately and clearly communicates the nature of the research to be done and its associated risks and benefits.

Appendix 1 Performance Status Criteria

| ECOG (Zubrod) Performance Status Scale | |
|---|--|
| Grade | Descriptions |
| 0 | Normal activity Fully active, able to carry on all pre-disease performance without restriction |
| 1 | Symptoms, but ambulatory Restricted in physically strenuous activity, but ambulatory and able to carry out work of a light or sedentary nature (e.g., light housework, office work) |
| 2 | In bed < 50% of the time Ambulatory and capable of all self-care, but unable to carry out any work activities Up and about more than 50% of waking hours |
| 3 | In bed > 50% of the time Capable of only limited self-care, confined to bed or chair more than 50% of waking hours |
| 4 | 100% bedridden Completely disabled Cannot carry on any self-care Totally confined to bed or chair |
| 5 | Dead |

Appendix 2 Data and Safety Monitoring Plan for Multicenter Institutional Study (Phase 2 or 3 Institutional Study)

The UCSF Helen Diller Family Comprehensive Cancer Center (HDFCCC) Data and Safety Monitoring Committee (DSMC) is responsible for monitoring data quality and subject safety for all HDFCCC institutional clinical studies. A summary of DSMC activities for this study includes:

- Review of subject data
- Review of suspected adverse reactions considered “serious”
- Monthly monitoring (depending on study accrual)
- Minimum of a yearly regulatory audit

Monitoring and Reporting Guidelines

All institutional Phase 2 or 3 therapeutic studies are designated with a moderate risk assessment. The data is monitored every six months, with twenty percent of the subjects monitored (or at least three subjects if the calculated value is less than three).

The UCSF Coordinating Center provides administration, data management, and organizational support for the participating sites in the conduct of a multicenter clinical trial. The UCSF Coordinating Center will also coordinate quarterly conference calls with the participating sites to communicate the review of adverse events, safety data, and other study matters.

The Principal Investigator at the UCSF Coordinating Center will hold the role of Study Chair. The Study Chair is responsible for the overall conduct of the study and for monitoring its safety and progress at all participating sites. The Study Chair will conduct continuous review of data and subject safety and discuss each subject’s treatment at monthly UCSF Site Committee meetings. The discussions are documented in the UCSF Site Committee meeting minutes.

Multicenter communication

The UCSF Coordinating Center provides administration, data management, and organizational support for the participating sites in the conduct of a multicenter clinical trial. The UCSF Coordinating Center will also coordinate, at minimum, monthly conference calls with the participating sites at the completion of each cohort or more frequently as needed to discuss risk assessment. The following issues will be discussed as appropriate:

- Enrollment information
- Adverse events (i.e. new adverse events and updates on unresolved adverse events and new safety information)
- Protocol violations
- Other issues affecting the conduct of the study

Adverse events reporting to the DSMC will include reports from both the UCSF Coordinating Center, as well as the participating sites. The DSMC will be responsible for monitoring all data entered in OnCore® at the UCSF Coordinating Center and the participating sites. The data (i.e. copies of source documents) from the participating sites will be sent electronically or faxed over to the UCSF Coordinating Center prior to

the monitoring visits in order for the DSMC to monitor the participating site's compliance with the protocol, patient safety, and to verify data entry.

Adverse Event Review and Monitoring

Adverse Event Monitoring

All Grade 3-5 Adverse Events, whether or not unexpected, and whether or not considered to be associated with the use of study drug, will be entered into OnCore[®], UCSF's Clinical Trial Management System.

All Grade 3-5 adverse events entered into OnCore[®] will be reviewed on a monthly basis at the UCSF Site Committee meetings. All clinically significant adverse events must be reported to the UCSF Coordinating Center by the participating sites within 10 business days of becoming aware of the event or during the next scheduled quarterly conference call, whichever is sooner. The UCSF Site Committee will review and discuss the selected toxicity, the toxicity grade, and the attribution of relationship of the adverse event to the administration of the study drug(s) from the UCSF Coordinating Center and the participating sites.

